5.2 VISIT SCHEDULE

	Visit 1 (V1) Screening / Baseline	Visit 2 (V2) (2-10 days after V1)	Visit 3 (V3) (10-24 days after V2)	Visit 4 (V4) (1 day after V3)	Visit 5 (V5) (6±1 days after V4)
Informed Consent	X				
Check Inclusion/exclusion criteria	X				
Demographics, medical history	X				
Concomitant medication	X				
Vital signs	X	X	X	X	X
Height	X				
Weight	X	X			X
Physical examination	X		X		X
ECG	X		X		
Blood sampling for platelet activity parameters		X	X	X	X
Blood sampling for hormones		X	X	X	X
Blood cell count	X				X
HbA1c	X				
Lipids	X	X			X
Liver function parameters (AST, ALT, GGT)	X				X
Renal function parameters (creatinine, eGFR)	X				X
Serology for Hepatitis B, C and HIV	X				
Pregnancy test (in female)	X		X		
Adverse Events		X	X	X	X
Hyperinsulinemic-Euglycemic Clamp investigation		X			
Hyperinsulinemic-Hypoglycemic Clamp investigation			X		

Table 1. Study related investigations

5.2.1 Visit 1

- Obtain informed consent of potential participant verified by signature on the study informed consent form
- Collect blood to check for inclusion criteria (Blood count, HbA1c, glucose, lipids, renal and liver function parameters)
- Collect and prepare blood samples for biobank
- Obtain demographic information, medical history, medication history
- Record vital signs

 endocrinology diabetology	Title: DIAPLATE-STUDY	Protocol No: Version 3.5	Sponsor: Medical University of Graz	Date: 13th February 2018
---	--------------------------	-----------------------------	--	-----------------------------

- Perform ECG
- Measure body weight and body height, calculate BMI
- Perform physical examination
- Verify inclusion/exclusion criteria

5.2.2 VISIT 2 – HYPERINSULINEMIC-EUGLYCEMIC CLAMP (2-10 DAYS AFTER VISIT 1)

The hyperinsulinemic – euglycemic clamp will be performed at visit 2. Patients will be advised to attend to the study center (Clinical Research Center [CRC], [name], 8010 GRAZ) at 06:30 am after an overnight 10 hours fasting period. In case of antidiabetic treatment with Metformin, the morning dose should not be administered. Vital signs will be determined and possible Adverse Events will be documented. Patients will be advised to place in the study bed in which they will remain during the whole clamp experiment.

At approximately 07:00 in the morning, two intravenous cannulas (catheters) will be inserted: one cannula will be inserted in an antecubital vein of a forearm for sampling of serial measurements of plasma glucose (approximately every 5-30 min, depending on the clamp procedure and safety). The hand will be placed in a heated environment to enable drawing of arterialised-venous blood. For controlled variable infusion of glucose 20% and infusion of human soluble insulin (40 IU Actrapid®, 100 IU/ml in 99.6 mL saline), an antecubital vein of the contralateral arm will be cannulated. Both cannulas will be kept open by a slow continuous 0.9% saline infusion. After the baseline blood samples for blood glucose, insulin and platelet activity have been taken (timepoint 0 min), the hyperinsulinemic – euglycemic clamp will be started. A variable i.v. infusion of glucose 20% or infusion of human soluble insulin will be initiated in order to obtain a plasma glucose target of 5.5 mmol/L (100 mg/dL) \pm 10%. The insulin infusion should be stopped completely if glucose has to be infused and vice versa. When the plasma glucose target of 5.5 mmol/L (100 mg/dL) \pm 10% is reached, a continuous insulin infusion (2.5 mU/kg/min) of human soluble insulin will be applied for 120 min to acutely raise and maintain serum insulin concentrations. Blood glucose will be clamped at the concentration of 5.5 mmol/L by a variable infusion of glucose 20%. Blood samples for measurement of plasma glucose concentrations will be obtained at 5 min interval, for measurement of insulin concentrations and platelet activity every 30 min (timepoints 0, 60, 90, 120 min.) throughout the clamp. For safety reasons, serum potassium will be measured at start of the clamp procedure and after that at the discretion of the investigator. Potassium will be substituted at discretion of the investigator. After 120 min, the clamp experiment is completed. Subjects will receive a meal and will remain at the study center until stabilisation of PG. When patients are in a normoglycemic state and in a good clinical condition, determined by the investigator, they will be discharged equipped with carbohydrates for hypoglycemia prevention.

	Title: DIAPLATE-STUDY	Protocol No: Version 3.5	Sponsor: Medical University of Graz	Date: 13th February 2018
--	--------------------------	-----------------------------	--	-----------------------------

5.2.3. VISIT 3 – HYPERINSULINEMIC-HYPOGLYCEMIC CLAMP (10-24 DAYS AFTER VISIT 1)

[figure not shown]
The hyperinsulinemic-hypoglycemic clamp will be performed at Visit 3. Patients will be advised to attend to the study center (Clinical Research Center [CRC], [name], 8010 GRAZ) at 06:30 am after an overnight 10 hours fasting period. In case of antidiabetic treatment with Metformin, the morning dose should not be administered. Vital signs will be determined and documented, females with child bearing potential will do a pregnancy test and a physical status will be performed by the physician in charge, and possible Adverse Events will be documented. Patients will be advised to place in the study bed in which they will remain during the whole clamp experiment. Then, pulse and blood pressure monitoring will start.

At approximately 07:00, two intravenous cannulas (catheters) will be inserted: one cannula will be inserted in an antecubital vein of a forearm for sampling of serial measurements of plasma glucose (approximately every 5-30 min, depending on the clamp procedure and safety). The hand will be placed in a heated environment to enable drawing of arterialised-venous blood. For controlled variable infusion of glucose 20% and infusion of human soluble insulin (40 IU Actrapid®, 100 IU/ml in 99.6 mL saline), an antecubital vein of the contralateral arm will be cannulated. Both cannulas will be kept open by a slow continuous 0.9% saline infusion. After the baseline blood samples for blood glucose, insulin, counter regulatory hormone parameters and platelet activity have been taken, the hyperinsulinemic hypoglycemic clamp will be started. A variable i.v. infusion of glucose 20% or infusion of human soluble insulin will be initiated in order to obtain a plasma glucose target of 5.5 mmol/L (100 mg/dL) \pm 10%. When the plasma glucose target of 5.5 mmol/L (100mg/dL) \pm 10% is reached the high constant insulin infusion (2.5 mU/kg/min) will be initiated. After 30 minutes the plateau 5.5mmol/L will be started. After 30 min on the 5.5 mmol/L plateau the glucose infusion will be interrupted, the PG will be allowed to decline to 3.5 mmol/L and by restarting the variable glucose infusion, kept stable at 3.5 mmol/L. Thereafter the glucose infusion will be interrupted and the PG will be allowed to decline to 2.5 mmol/L or a nadir at a higher concentration in case 2.5 mmol/L cannot be reached or symptoms of hypoglycaemia are unacceptable. By restarting the variable glucose infusion the PG will be kept stable at 2.5 mmol/L or nadir and assessments on the plateau will be performed. After 15 min on the 2.5 mmol/L or nadir plateau the constant high insulin infusion will be terminated. Starting at time point 25 min on the 2.5 mmol/L or nadir plateau the glucose infusion will be tapered off, if possible, to allow a spontaneous recovery from hypoglycaemia. PG will not be allowed to fall below 2.2 mmol/L. If PG has not reached 4.0 mmol/L 45 min after termination of the constant high insulin infusion, a constant high glucose infusion (5.5 mg/kg/min) will be initiated to increase PG to a level of 4.0 mmol/L. When reaching the PG level of 4.0 mmol/L assessments will be performed and blood samples will be taken. The PG will then be increased to 5.5 mmol/L for safety reasons and the clamp terminated, if deemed safe by the investigator. PAP and CRH samples will be obtained at the end of each plateau phase as well as after recovery from hypoglycaemia at PG 100mg/dl (see figure 1).

	Title: DIAPLATE-STUDY	Protocol No: Version 3.5	Sponsor: Medical University of Graz	Date: 13th February 2018
--	--------------------------	-----------------------------	--	-----------------------------

After initiation of the high constant insulin infusion potassium concentration will be measured at the discretion of the investigator and potassium replaced if necessary. ECG will be continuously monitored during the clamp procedure using patient cardiac monitoring system “Dräger”. One 12-lead ECG will be recorded during run-in phase (before starting constant high insulin infusion) and at hypoglycaemia or nadir of 2.5 mmol/L at approximately 15 min. In case a subjects PG does not decrease from 5.5 mmol/L to 3.5 mmol/L within 30 minutes, the 3.5 mmol/L assessment plateau will be initiated in any case after 30 minutes after the end of assessment plateau 5.5 mmol/L high insulin. In case a subjects PG does not decrease from 3.5 mmol/L to 2.5 mmol/L within 30 minutes, the 2.5 mmol/L assessment plateau will be initiated in any case after 30 minutes after the end of assessment plateau 3.5 mmol/L. In the above cases, the glucose infusion should not be initiated at the start of the assessment plateaus to allow a further decrease in PG levels to the scheduled target PG levels. Subjects will receive a meal and will remain at the study center until stabilisation of PG. When patients are in a normoglycemic state and in a good clinical condition, determined by the investigator, patients will be discharged home.

Figure 1. Hyperinsulinemic-Hypoglycemic Clamp with time points of sampling collection

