5.2.3 VISIT 4 – FOLLOW-UP VISIT (ONE DAY AFTER THE CLAMP EXPERIMENT)

 endocrinology diabetology	Title: DIAPLATE-STUDY	Protocol No: Version 3.5	Sponsor: Medical University of Graz	Date: 13th February 2018
---	--------------------------	-----------------------------	--	-----------------------------

Visit 4 will be performed for a follow up one day after the clamp investigation. Vital signs will be recorded and possible adverse events will be raised and documented. Then venous blood sampling will be performed for PAP and CRH.

Visit procedures:

- Record vital signs
- Collect blood for platelet activation parameters
- Collect blood for counter regulatory hormones
- Collect and prepare blood samples for biobank
- Record adverse events as reported by participant or observed by investigator

5.2.4 VISIT 5 - FOLLOW-UP VISIT (6±1 DAYS AFTER VISIT 4 - CLOSE OUT VISIT)

This visit will take place 6±1 days after the clamp experiment. Vital signs will be recorded, a physical examination will be performed and possible adverse events will be raised and documented. Additionally to the measurements at Visit 4 blood for blood count and chemistry will be sampled, as well as body weight will be determined.

Visit procedures:

- Record adverse events as reported by participant or observed by the investigator
- Record vital signs
- Collect blood for routine biochemistry
- Collect blood for platelet activity parameters
- Collect blood for counter regulatory hormones
- Collect and prepare blood samples for biobank
- Perform physical examination
- Determination of body weight

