6.6. ADVERSE EVENTS RELATED TO THE CLAMP EXPERIMENT

The trial will include a hypoglycaemic clamp procedure during Visit 3. Within the clamp experiment hypoglycaemia is intentionally induced. Depending on potency of hypoglycaemia patients might feel discomfort, sweating, lack of concentration, dizziness, palpitations, or general discomfort. Hypoglycaemia will

	Title: DIAPLATE-STUDY	Protocol No: Version 3.5	Sponsor: Medical University of Graz	Date: 13th February 2018
--	--------------------------	-----------------------------	--	-----------------------------

be controlled by frequent venous glucose measurements. In case of unacceptable or unbearable hypoglycaemia during the clamp procedure, glucose will be administered and clamp investigation will be terminated if deemed necessary for the investigator or the subject wants to break up. During the entire clamp experiment, patients will be continuously monitored for glucose, heart rate, blood pressure and potassium. Medical staff is highly experienced and qualified for performing clamp investigations. The clamp may be interrupted or terminated for safety reasons at any time at the investigators discretion.

Independently from hypoglycaemia related adverse event, some discomfort may occur as a result from vein puncture or venous line issues. In some cases local haematoma can occur, very seldom installed venous lines might lead to local infection and phlebitis of the punctured vein which may require local and/or systemic treatment.

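### Discharge after the hypoglycaemic clamp (Visit 3) omits the take-home carbohydrates that the protocol provides after the euglycaemic clamp (Visit 2)

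*Combined protocol and SAP*

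**What the plan says.** Section 5.2.2 (Visit 2, euglycaemic clamp) closes with the sentence "Subjects will receive a meal and will remain at the study center until stabilisation of PG", and section 5.2.3 (Visit 3, hypoglycaemic clamp) repeats it. The two sections then set the same clinical condition for leaving and differ only in how the sentence ends:

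- Visit 2: "When patients are in a normoglycemic state and in a good clinical condition, determined by the investigator, they will be discharged equipped with carbohydrates", and the stated purpose of the carbohydrates is to prevent hypoglycaemia.
- Visit 3: "When patients are in a normoglycemic state and in a good clinical condition, determined by the investigator, patients will be discharged home".

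Three other places bear on the point. Section 6.6 says of Visit 3 that "Within the clamp experiment hypoglycaemia is intentionally induced". It also says that "During the entire clamp experiment, patients will be continuously monitored for glucose, heart rate, blood pressure and potassium", which covers the clamp but not the time after discharge. Section 5.2.3 describes the end of the Visit 3 clamp: "The PG will then be increased to 5.5 mmol/L for safety reasons and the clamp terminated, if deemed safe by the investigator". At Visit 4, the next day, "possible adverse events will be raised and documented".

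**The concern.** At Visit 2 the sponsor judged that a meal, stable glucose, normoglycaemia and the investigator's assessment were worth supplementing with carbohydrates to take home. The same four safeguards apply at Visit 3, so they cannot be the reason for leaving the carbohydrates out there. Visit 3 uses the same constant insulin rate and is the visit at which glucose is deliberately lowered, so one would expect at least the same provision.

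Section 10.6 asks that the approved protocol be followed at all times. A site that does so has no instruction to hand out carbohydrates after Visit 3. What is at stake is a small, cheap protection for subjects on the way home. No estimate, test or endpoint depends on it.

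**Working it through.** The plan states no figure on this point, so the check is a comparison of texts, followed by simple arithmetic to see whether insulin dose could explain the difference.

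**Comparison of the two discharge texts**

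| Element | Visit 2 (5.2.2) | Visit 3 (5.2.3) |
|---|---|---|
| Meal | yes | yes |
| Stay until glucose is stable | yes | yes |
| Normoglycaemia | yes | yes |
| Good condition, investigator's judgement | yes | yes |
| Carbohydrates to take home | yes | not mentioned |

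The rest of the supplied text does not fill the gap. Section 6.6 provides for glucose during the clamp if hypoglycaemia becomes unacceptable. The Visit 4 text covers the next-day visit.

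**Constant insulin dose**

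Formula: dose = rate × minutes. The rate is 2.5 mU/kg/min at both visits (5.2.2 and 5.2.3). Variable insulin given before the constant infusion is not quantified and is left out for both visits.

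- *Visit 2.* The duration is 120 min (5.2.2). Dose = 2.5 × 120 = 300 mU/kg = 0.30 U/kg.
- *Visit 3, stated fixed times only.* There are 30 min before the 5.5 mmol/L plateau, 30 min on it, and 15 min on the 2.5 mmol/L plateau before insulin stops: 30 + 30 + 15 = 75 min. Dose = 2.5 × 75 = 187.5 mU/kg, about 0.19 U/kg. This is a floor, because it allows no time for either fall in glucose or for the 3.5 mmol/L plateau.
- *Visit 3, adding both 30-minute limits on the falls in glucose (5.2.3).* 75 + 60 = 135 min. Dose = 2.5 × 135 = 337.5 mU/kg, about 0.34 U/kg.
- *Visit 3, also adding the 3.5 mmol/L plateau.* The readable text does not give its length and Figure 1 is not shown, so 30 min is an assumption. 135 + 30 = 165 min. Dose = 2.5 × 165 = 412.5 mU/kg, about 0.41 U/kg. With an assumed 15 min plateau the total is 150 min and 0.375 U/kg.

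Break-even with Visit 2: 120 − 75 = 45 min. Visit 3 gives more constant insulin than Visit 2 only if the two falls plus the 3.5 mmol/L plateau last more than 45 min in total.

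The Visit 3 range, 0.19 to 0.41 U/kg, lies on both sides of the Visit 2 dose of 0.30 U/kg. Dose therefore gives no clear reason to drop the carbohydrates, and equally no evidence that Visit 3 is the riskier discharge.

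**The case against.** The strongest reply is that the two clamps end differently. At Visit 2 the insulin runs to the end of the 120 minutes and no recovery phase is described. At Visit 3 insulin stops 15 min into the lowest plateau and the glucose infusion is tapered from 25 min. If glucose has not reached 4.0 mmol/L 45 min after insulin stops, a constant high glucose infusion is started. Glucose is then raised to 5.5 mmol/L before the clamp is closed. Total dose ignores this longer time off insulin. The difference in design stands and could partly explain the omission, but the protocol does not give it as a reason, and both visits also require a further stay until glucose is stable.

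A second reply is that the subjects are at low risk. They take metformin or follow diet only, and section 4.2 excludes impaired hypoglycaemic awareness and a severe event needing third-party help in the last 6 months. That is true, but it applies equally at Visit 2, where carbohydrates are still provided.

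A third reply is that silence is not prohibition. Staff may hand out carbohydrates anyway, and the consent pages, which might contain discharge advice, are not in the supplied text. This also stands: the point concerns what the protocol body instructs, not what happens in practice.

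None of these replies accounts for the difference in wording. They do keep the point small.

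**Conclusion.** The concern holds as a minor participant-safety point. The discharge conditions are the same at both clamp visits, and the take-home carbohydrates appear only after the one that does not induce hypoglycaemia. The protocol gives no reason.

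All 14 planned subjects, or up to 16 with the allowance for drop-outs in section 7.1, would be discharged under the Visit 3 text. The number who might benefit cannot be estimated, because the documents give no rate of hypoglycaemia after discharge. No excess risk after Visit 3 is claimed. The primary endpoint is measured within that visit, before discharge, and is not affected. The Visit 4 adverse event enquiry can already pick up an episode on the way home or overnight.

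Confidence in the textual mismatch is high. The upper dose figure rests on the assumed 30 min plateau at 3.5 mmol/L, but the conclusion does not depend on it.

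**What to change.** In section 5.2.3 (Visit 3), extend the discharge sentence with the closing phrase of the Visit 2 sentence, so that subjects also go home with carbohydrates to prevent hypoglycaemia. No other change is needed.

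The cost is one phrase in the protocol and take-home carbohydrates for 14 to 16 subjects. There is no extra visit, sample or question, and no change to the design or the analysis.

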5.2.3 VISIT 4 – FOLLOW-UP VISIT (ONE DAY AFTER THE CLAMP EXPERIMENT)

 endocrinology diabetology	Title: DIAPLATE-STUDY	Protocol No: Version 3.5	Sponsor: Medical University of Graz	Date: 13th February 2018
---	--------------------------	-----------------------------	--	-----------------------------

Visit 4 will be performed for a follow up one day after the clamp investigation. Vital signs will be recorded and possible adverse events will be raised and documented. Then venous blood sampling will be performed for PAP and CRH.

Visit procedures:

- Record vital signs
- Collect blood for platelet activation parameters
- Collect blood for counter regulatory hormones
- Collect and prepare blood samples for biobank
- Record adverse events as reported by participant or observed by investigator

5.2.4 VISIT 5 - FOLLOW-UP VISIT (6±1 DAYS AFTER VISIT 4 - CLOSE OUT VISIT)

This visit will take place 6±1 days after the clamp experiment. Vital signs will be recorded, a physical examination will be performed and possible adverse events will be raised and documented. Additionally to the measurements at Visit 4 blood for blood count and chemistry will be sampled, as well as body weight will be determined.

Visit procedures:

- Record adverse events as reported by participant or observed by the investigator
- Record vital signs
- Collect blood for routine biochemistry
- Collect blood for platelet activity parameters
- Collect blood for counter regulatory hormones
- Collect and prepare blood samples for biobank
- Perform physical examination
- Determination of body weight

5.3 DESCRIPTION OF PROCEDURES AND MEASUREMENTS

5.3.1 MEDICAL HISTORY AND PHYSICAL EXAMINATION

Determination of medical history will be performed at the screening visit to record illnesses, health disorders and concomitant medication. Physical examination will be performed at the Screening visit 1, visit 3 as well as at the closing visit according to local procedure. The physician will perform the physical examinations with the focus on cardiac, lung and abdominal examination. Any abnormal, clinical significant findings must be recorded in the SDF. Any adverse events will be recorded. Any changes in medications will be recorded in the SDF.

	Title: DIAPLATE-STUDY	Protocol No: Version 3.5	Sponsor: Medical University of Graz	Date: 13th February 2018
--	--------------------------	-----------------------------	--	-----------------------------

5.3.2 ELECTROCARDIOGRAPHY

An ECG will be performed at the screening visit. The ECG will be interpreted, signed and dated by the investigator. ECG will be continuously monitored during visit 3.

5.3.3 VITAL SIGNS

Pulse should be recorded at all visits after resting for five minutes in a sitting position. Systolic and diastolic blood pressure will be measured in sitting position at all visits.

5.3.4 BODY WEIGHT AND HEIGHT

Weight should be measured at the screening and closing visit, as well as at visit 2. The same and calibrated pair of scales should preferably be used throughout the trial.

Height will be recorded at the screening visit. BMI (body mass index) will be calculated as follows: $BMI = \frac{\text{weight}}{(\text{kg})/\text{height}^2 (\text{m}^2)}$.

5.3.5 ROUTINE BIOCHEMISTRY

Blood samples will be obtained at all visits in the fasting state and processed by the local laboratory using standard methods for routine tests. Patients can take their regular morning medications but are asked that they do not take metformin in case of a concomitant metformin therapy. Patients should bring their regular medication along to their study visits to be further advised by the doctor. See table below for a detailed description of blood collection at each visit.

5.3.6 BLOOD SAMPLE COLLECTION AND PLASMA EXTRACTION FOR BIOBANKING

Blood will be collected via venous puncture into 8 ml serum and 6 ml EDTA vacutainers and centrifuged within 30 min of collection. Plasma should be transferred into Eppendorf tubes and stored at -80 °C locally.

